6.4 Sample Size and Power

The current study is a pilot that is seeking to test the acceptability and feasibility of an intervention to increase sleep during HSCT. 16 subjects will yield an adequate sample size for a pilot study³⁰ to estimate effect sizes for a future trial.

7 STUDY INTERVENTION

7.1 Description

For the 5 day-intervention period, the study staff will work with the subject's nurse to plan on 6-hour extended period between vitals checks, occurring overnight. On each intervention night, the research team will verify with the child's oncology provider that it is acceptable for the patient to have a 6-hour window between vitals checks. This confirmation will be communicated to the child's nighttime nurse. For the 5 days of the child's intervention period, the nurse will be instructed to conduct the last vitals check between 9pm-1am. After the last vitals check, the patient will be given 6 hours until the next vitals check, unless the caregiver/patient request nursing.

8 SAFETY MANAGEMENT

8.1 Clinical Adverse Events

Clinical adverse events (AEs) will be monitored throughout the study.

8.2 Adverse Event Reporting

Since the study procedures are not greater than minimal risk, SAEs are not expected. If any unanticipated problems related to the research involving risks to subjects or others happen during the course of this study (including SAEs) they will be reported to the IRB in accordance with CHOP IRB SOP 408: Unanticipated Problems Involving Risks to Subjects. AEs that are not serious but that are notable and could involve risks to subjects will be summarized in narrative or other format and submitted to the IRB at the time of continuing review.

9 STUDY ADMINISTRATION

9.1 Treatment Assignment Methods

9.1.1 Randomization

Participants will be randomized to either Observation/Intervention or Intervention/Observation on day +5 post-transplant. The research coordinator will generate a randomization sequence using a random number generator, with block randomization occurring based on participant age (8-12 or 13-21). Blinding will not be possible, but randomization will occur on day +5 to minimize the impact of the intervention on the initial observation period.

9.2 Data Collection and Management

Electronic health record data.

Investigators will generate a list of MRNs for participants with positive parental consent who have completed the survey. A trained research assistant with limited EHR access will extract treatment related data from the EHR. To obtain a password for the EHRs, all staff must complete training on the importance of patient privacy. Training on the Health Insurance Portability and Accountability Act (HIPAA) is required for all employees. With the EHRs, patient privacy is protected by multi-step, system wide processes. Anyone

wishing to view the charts of patients for whom they do not provide care must “break the glass.” This system requires a declaration of why the chart is being viewed and sends a message to both an employee’s supervisor and the hospital’s privacy officer. In summary, the inappropriate access to electronic health information is carefully monitored and strictly prohibited. All study files retained on CHOP’s secure network or within secure REDCap database will be accessed only by study staff using a CHOP issued, password-protected computer.

Child- and parent-report data:

Participants will complete daily sleep diary questions using REDCap and the integration with Twilio (a text messaging platform that integrates with REDCap). No PHI will be transmitted over text message. Electronic demographic, psychosocial, and acceptability surveys will also be obtained using REDCap. The CHOP Research Institute Center for Biomedical Informatics (CBMi) will be used as a central location for data processing and management. These data will be stored within REDCap by participant study ID.

Nurse acceptability data:

Nurses will complete acceptability questionnaires for each night they care for the child during the extended vitals check portion of the study using REDCap and the integration with Twilio (a text messaging platform that integrates with REDCap). No PHI will be transmitted over text message. The CHOP Research Institute Center for Biomedical Informatics (CBMi) will be used as a central location for data processing and management. These data will be stored within REDCap by participant study ID.

Confidentiality of On-Line Assessment.

Participants will complete self-report questionnaires through internet access to REDCap. Daily text messages will be completed and stored within REDCap via the integration with the text messaging platform Twilio. No PHI will be transmitted over text message. Participants will complete questionnaires that are only identified with a unique Study ID, which will be assigned during recruitment. The CHOP Research Institute Center for Biomedical Informatics (CBMi) will be used as a central location for data processing and management. CBMi represents CHOP in a consortium of over three hundred academic research institutions led by Vanderbilt University. Vanderbilt, with assistance from the consortium, has developed a software toolset and workflow methodology for electronic collection and management of research and clinical trial data. REDCap (Research Electronic Data Capture) data collection projects rely on a thorough study-specific data dictionary defined in an iterative self-documenting process by all members of the research team with planning assistance from CBMi. The iterative development and testing process results in a well-planned data collection strategy for individual studies. REDCap is also a powerful tool for building and managing online surveys. The research team can create and design surveys in a web browser and engage potential respondents using a variety of notification methods. REDCap provides secure, web-based applications that are flexible enough to be used for a variety of types of research, provide an intuitive interface for users to enter data and have real time validation rules (with automated data type and range checks) at the time of entry. These systems offer easy data manipulation with audit trails for reporting, monitoring, and querying patient records, and an automated

export mechanism to common statistical packages (SPSS, SAS, Stata, R/S-Plus). Within REDCap, all data are stored by study ID number only.

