| HSCT | Hematopoietic stem cell transplant |
| HRQL | Health-related quality of life |
| AE | Adverse event |
| EHR | Electronic Health Record |
| MRN | Medical Record Number |

ABSTRACT

Context: Patients undergoing treatment for cancer face disease, treatment, and environmental obstacles to sufficient, sound sleep¹. Hospitalizations can further worsen sleep quality and quantity due to overnight vitals checks, medication administration, blood draws, and environmental noise and light². For patients undergoing hematopoietic stem cell transplant (HSCT), the risk for poor sleep is especially high due to protracted hospitalization, frequent vitals checks resulting in multiple night awakenings³, and high symptom burden peaking approximately 10 days post-transplant⁴.

Objectives:

Primary: Test the acceptability and feasibility of protecting one 6-hour window for nighttime sleep (intervention) relative to regular vitals checks (observation only periods) during HSCT recovery.

Secondary: Assess the effect of one 6-hour window for nighttime sleep on subject sleep and engagement in supportive care on the HSCT unit.

Study Design:

Aggregated N=1 randomized controlled design. All participants will undergo a 5 day observation and then be randomized to receive the 5 day intervention (extended vitals checks) during either nights of days +5-+9 or days +10-+14.

Setting/Participants:

Inpatients on the HSCT Unit at CHOP

Study Interventions and Measures:

[figure not shown]
Intervention—increasing time between vitals checks from every 4 hours to one 6-hour period at night.

Subjects will wear an actigraph for the duration of the study, complete a daily sleep diary, and complete self- and parent-proxy psychosocial measures (symptom burden, health related quality of life, sleep) and acceptability. Medical record review will also be conducted to assess vitals check frequency.

TABLE 1: SCHEDULE OF STUDY PROCEDURES

| Visit | Purpose | Main Procedures | Duration |
|--------------------------------|--------------------------|--|------------|
| Visit 1 Pre-transplant | Baseline measures | Complete Informed consent Complete CEFIS Complete self-report measures Give actigraph | 35 minutes |
| Visit 2, Transplant Day 0 | Start actigraph | Review actigraphy procedures | 5 minutes |
| Visit 3, Transplant Day +5 | Randomization | Randomize to intervention start Complete self-report measures | 20 minutes |

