3.4 Study Population

3.4.1 Inclusion Criteria

(Patient Subjects)

- 1) Males or females age 8 to 21 years.
- 2) Undergoing HSCT at The Children's Hospital of Philadelphia
- 3) Parent/guardian permission (informed consent) and if appropriate, child assent.

(Nurse Subjects)

- 4) HSCT Nurse working night shift during subject's extended vitals check.

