4.2.1 Visit 1 Day -2 to Day -1 before transplant

- Informed Consent
- Medical Record Review
- Demographic, COVID-19 Impact measure, and Psychosocial Measures (Symptom Burden, HRQL, and Sleep)
- Introduce actigraph and electronic sleep diary.

4.2.2 Visit 2 Day 0

- Place actigraph on patient's non-dominant wrist. Patient is asked to wear the actigraph for the duration of the study (morning of Day 0- the night of Day +14). The patient can remove the actigraph upon awakening on Day +15.
- Review actigraph and electronic sleep diary procedures.

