5 STUDY EVALUATIONS AND MEASUREMENTS

5.1 Screening and Monitoring Evaluations and Measurements

5.1.1 Medical Record Review

Include a listing of the variables that will be abstracted from the medical chart (paper or electronic).

- Date of birth
- Date of diagnosis and treatment history
- Medications
- Length of hospitalization prior to starting the study
- Number of visits completed or declined with supportive services (physical therapy, occupational therapy, school, creative arts therapies, and/or psychology) for each study period (Days 0-+4 including nights, Days +5-+9 including nights, Days +10-+14 including nights).
- Frequency and timing of vitals checks for each day in the study.
- Medications used for supportive care for each study period (Days 0-+4 including nights, Days +5-+9 including nights, Days +10-+14).
- Transplant parameters including: type of transplant, disease status, cell processing, GVHD prophylaxis and infectionus prophylaxis.

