5.1.2 Other Evaluations, Measures

Subjects and caregivers will complete the following measures:

| Table 1. Study Measures. | | Baseline | Day +5 | Day +10 | Day +15 |
|--------------------------|--|----------|--------|---------|---------|
| Construct | Measure | | | | |
| Acceptability | Patient, caregiver, and nurse will respond to a brief questionnaire of acceptability of adjusting vitals checks. | | | | x |
| Demographics | Report of sex, race/ethnicity, age of child and caregiver | x | | | |
| COVID-19 Impact | COVID-19 Exposure and Family Impact Survey (CEFIS) to assess family exposure to and experience with COVID-19 through Yes/No responses (25 items); 12 items assessing the impact of the pandemic on | x | | | |

| | | | | | |
|---------------------------|---|---|---|---|---|
| | self/family with 1-4 intensity scale and 1 open-ended item | | | | |
| HRQL and related symptoms | Pediatric Quality of Life Inventory—Stem Cell Transplant Module. This measure assesses HRQL and symptoms relevant to patients undergoing HSCT. The measure includes questions about pain, fatigue/sleep, nausea, communication, worry, nutrition, thinking and other symptoms answered on parallel child and adolescent with parent proxy forms (41 items). ²⁶ | x | x | x | x |
| Sleep | PROMIS Sleep Measures—Sleep disturbance, sleep-related impairment, and sleep hygiene over the past week-parallel parent/child forms (24 items) ²⁷ . | x | x | x | x |
| Supportive Care Use | EHR review to document engagement or refusal of PT/OT/School/Creative Art Therapy/ Psychology for each 5 day period. | | x | x | x |
| Actigraphy | Worn by participant day 0-night of Day +14, removing on awakening on Day+15. To validate actigraphy: bedtime, waketime, night awakenings, naps, time actigraph was off reported daily through text messages delivered via REDCap and its integration with Twilio. | | | | |

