9.5 Recruitment Strategy

After IRB approval, potential patient participants will be identified through the CHOP Stem Cell Transplant list and cleared by the patient's primary oncologist. Potential participants will be invited to participate in the study during family education day prior to the stem cell transplant admission. Families will be given the "Fast Facts" flyer about the study.

To enable the study coordinator scheduling and to allow for the extraction of EHR data, it will be necessary to maintain a "tracking" database that contains information about potentially eligible participants (e.g., parent name, child name, appointment time and location, date of birth, and MRN). Potential participant information will be added to the database from the Stem Cell Transplant List and will be updated through weekly chart review. This database will be maintained on a CHOP password-protected computer. All potential participants will be randomly assigned a participant ID number when their information is entered into the tracking database.

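### Section 9.2 ties EHR extraction to parental consent and an unnamed survey; read literally it omits self-consenting adults and leaves the basis of EHR-measured compliance unclear

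*Combined protocol and SAP*

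**What the plan says.** Section 9.2 opens its EHR paragraph with the rule "Investigators will generate a list of MRNs for participants with positive parental consent who have completed the survey". A research assistant then extracts treatment data from the EHR. Later in the same section, several surveys are named: "Electronic demographic, psychosocial, and acceptability surveys will also be obtained using REDCap".

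On who may take part, Section 3.4.1 admits "Males or females age 8 to 21 years". Section 9.6 has parents or guardians consent for patients under 18, and patients of 18 or over consent for themselves, with HIPAA authorisation combined with consent.

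Record review is described in seven other places, none with a survey condition:
- Abstract: "Medical record review will also be conducted to assess vitals check frequency".
- Section 4.2.1, Visit 1: "Medical Record Review", listed beside consent and the baseline measures.
- Section 5.1.1: "Frequency and timing of vitals checks for each day in the study", with supportive-care visits counted for each of the three study periods.
- Section 5.1.2, measures table: "EHR review to document engagement or refusal of" the supportive services, per 5-day period.
- Section 6.1: EHR review is the source for compliance with extended vitals checks.
- Section 6.2: EHR review is the source for supportive-care engagement.
- Section 9.5, on the recruitment tracking database: "to allow for the extraction of EHR data, it will be necessary to maintain" such a database.

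**The concern.** Section 9.2 is the only place that states how charts are selected for extraction. Followed as written, it selects on two conditions. The first, parental consent, does not fit a trial that lets adult patients consent for themselves. The second, completion of a survey, is undefined, and at some of its possible meanings it selects on something that happens after the intervention has started.

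The EHR is the only named source for two measures: compliance with the 6-hour window, which is one of the two feasibility components of the primary endpoint, and engagement in supportive care. If the list is selected, so are these measures, and a reader of the report could not tell who is missing, because no section states a denominator for compliance.

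A related wording problem sits in Section 6.1. Medical eligibility is to be documented on each day that is already described as eligible. Taken as the base of an eligibility rate, that is circular.

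**Working it through.** The plan gives no figure to reproduce, so the check is mainly a comparison of text. The arithmetic that follows only shows scale.

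**1. Consent condition.** Ages run from 8 to 21 (Section 3.4.1). Patients of 18 or over give their own consent (Section 9.6). A list restricted to parental consent therefore excludes patients aged 18 to 21 who consented for themselves. The two rules cannot both be applied literally.

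**2. Survey condition.** The possible meanings and their timing (Sections 4.2 and 5.1.2) are:

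| Meaning of the survey | When given | Effect on the list |
|---|---|---|
| Demographic form or baseline packet | Visit 1, Day -2 to -1 | Almost none: consent, baseline measures and record review share this visit |
| Psychosocial packet after baseline | Day +5, +10 or +15 | Keeps completers only |
| Patient acceptability survey | Day +15 | Keeps completers only |

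Under the last two meanings, selection could be related to the outcome. Section 4.4 allows discontinuation for poor adherence or a change in medical status, and either could go with fewer delivered nights. The direction cannot be derived from the documents.

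**3. Other sections.** Of the seven other descriptions of record review, none states the survey condition and none says that review applies regardless of it. They are silent.

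**4. Share of nights per omitted participant.** Each randomised participant has 5 scheduled intervention nights (Section 3.1.3). The numbers of participants are the 50 evaluable and 55 enrolled of Section 3.3.2 and the 16 of Section 6.4. It is an assumption that each is the number randomised.
- 50 × 5 = 250 nights; 5/250 = 2.0%
- 55 × 5 = 275 nights; 5/275 = 1.8%
- 16 × 5 = 80 nights; 5/80 = 6.25%

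With omitted share f and rate p among listed participants, the delivered/scheduled rate in all randomised participants lies between p(1 − f) and p(1 − f) + f, a width of f. At an assumed p = 80% with one participant omitted:
- f = 0.02: 0.80 × 0.98 = 78.4%, up to 78.4 + 2.0 = 80.4%
- f = 0.0625: 0.80 × 0.9375 = 75.0%, up to 75.0 + 6.25 = 81.25%

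**5. Omitting ages 18 to 21.** If ages were uniform (assumed), this group is 4 of 14 age-years: f = 4/14 = 28.6%. That is 50 × 0.286 = 14.3 of 50 participants, or 16 × 0.286 = 4.6 of 16. The shift in the reported rate is f × (difference in compliance between listed and omitted). For an assumed difference of −20 to +20 points it is 0.286 × 20 = 5.7 points either way.

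**The case against.** The strongest reply is that the harmless reading is also the natural one. Sections 3.1.1, 3.1.2 and 4.2.1 put consent, baseline measures and record review at the same pre-transplant contact, so completing the survey may simply mean being enrolled. Parental consent may likewise be shorthand: inclusion criterion 3 in Section 3.4.1 also mentions only parent or guardian permission, in the same list that admits patients up to 21, while Section 9.6 governs consent and covers adults. Even on the Day +15 reading, Section 4.4.1 asks people who withdraw to complete the acceptability measure, so withdrawal would not by itself remove anyone from the list. Section 9.2 is a data-handling paragraph and defines no analysis population.

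Much of this stands. A reader might infer that the other sections contradict 9.2, or that 9.2 shows EHR data will be lost. The documents support neither. The other sections omit the survey condition without denying it, and the one in 9.5 concerns a recruitment database. Section 9.2 does not say that no other chart will be opened.

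What the reply does not remove is that the rule, as written, misstates who has consented and rests on an unnamed survey. Shorthand elsewhere explains the slip but does not correct the operating instruction that staff would follow.

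**Conclusion.** The point holds as a low minor one. The firm inconsistency is parental consent in 9.2 against self-consent at 18 or over in 9.6. The survey condition is an undefined restriction: close to no effect if it means the baseline packet, and bias of unknown size and direction if it means a later survey.

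The figures are illustrations. The shares of 1.8%, 2.0% and 6.25% say only what part of the scheduled nights one participant represents. The 80% rate, the uniform ages and the 20-point difference are assumptions, so a reader should not take 5.7 points as an estimate of bias. The documents give no compliance rate and no count of people who would be omitted.

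The consequence is also limited by the design. Feasibility is analysed descriptively (Section 6.3.2) with no threshold to pass. Staff-documented eligibility and the acceptability ratings do not depend on the 9.2 list.

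**What to change.** In Section 9.2, replace the list rule with this: EHR data are extracted for all enrolled patient subjects with valid consent and authorisation (parent or guardian, or the patient's own if 18 or over), regardless of survey completion and, after withdrawal, as far as consent allows. The rule should say enrolled, not randomised. Randomisation is on Day +5, and Section 5.1.1 calls for record data from Day 0 to +4, which would otherwise be dropped for subjects lost before randomisation.

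In Sections 6.1 and 6.3.2, take all scheduled intervention nights of all randomised participants as the base for the eligibility and delivery rates, in place of days already called eligible. Reporting eligible/scheduled, delivered/eligible and delivered/scheduled nights would keep medical ineligibility apart from non-delivery.

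The cost is one sentence in 9.2, a short wording change in 6.1 and 6.3.2, possibly a few more charts to extract, and a possibly lower reported compliance figure. No clinical rule changes.

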9.3 Confidentiality

No identifiable data will be used for future study without first obtaining IRB approval. The investigator will obtain a data use agreement between the provider (the PI) of the data and any recipient researchers (including others at CHOP and Rutgers University) before sharing a de-identified data set (all dates and zipcodes will be removed).

9.4 Regulatory and Ethical Considerations

9.4.1 Data and Safety Monitoring Plan

An independent Data Safety and Monitoring Board will not be instituted due to the low degree of risk with this study. The PI will oversee all data collection through the implementation of standardized data collection procedures. Safety monitoring will include careful assessment and appropriate reporting of AEs as indicated below, and will also include a regular assessment of the number and type of serious AEs. Any serious AEs that might reasonably be due to the study will be reported to the CHOP IRB within 24 hours of its occurrence. Events that are not related to the study but classified as imminent risk to the subjects will be reported to the investigators and appropriate clinical referrals will be made.

9.4.2 Risk Assessment

The risks associated with this study are minimal and generally not in excess of those encountered in the hospital stay. Specifically, risks include: 1) breach of confidentiality; 2) discomfort from questions regarding cancer history and current symptoms; 3) inconvenience of study procedures. Because participants are assessed on a daily basis for whether they are medically able to participate in extended vitals checks, the medical risk for extending time between vitals checks by 2 hours is assumed minimal. If a participant develops a fever during the extended vitals checks portion of the study, there is a risk that it will not be detected for an additional 2 hours. All participants can contact their nurse at any time between vitals checks for usual care or concerns such as fever. All participants will be informed of these risks prior to participation and will be informed of the right to discontinue participation if they are uncomfortable with the study. If participants become upset, [name] (licensed clinical psychologist, Director of Psychosocial Services in Oncology at CHOP) will assess the level of distress of the patient and determine the need for additional psychosocial support.

